## 8. Early Discontinuation Updated:

• Vital signs (blood pressure, temperature, pulse, and respiratory rate), height, weight, full physical exam, clinical laboratory tests, ECG, use of concomitant medications, and adverse events should be obtained at discharge prior to release.

### 9.5 Serious Adverse Events Reporting

Updated: All SAEs must be reported immediately (within 24 hours of learning of the event) by telephone or notification via email through the via entry into the EDC system with at least the event term, start date, and IP relationship. In the event EDC entry is unavailable, notification must occur via email or phone to the contact below to:

[name] Cassava Sciences, Inc.

Email: [contact]

[contact]

Do not delay reporting a suspected SAE to obtain additional information. Any additional information, if collected, can be reported to the Sponsor as a follow-up to the initial report.

If a partial SAE report was initially provided then a A complete SAE report form must be entered into the EDC sent within five (5) working days to the medical monitor. The Investigator is responsible for reporting SAEs to the IRB according to IRB guidelines. The Sponsor will report SAEs to the IRB and FDA as required.

### 11. STUDY TERMINATION

**Updated**: The study will be terminated following <del>completion of the study FDA approval of simufilam or program termination</del> or at any time at the discretion of the Sponsor.

### Added:

15: Appendix A: Study Design Schematic

### Changed:

15: Appendix A: Schedule of Events to 16: Appendix B: Schedule of Events for Active Participants

### Added:

17: Appendix C: Schedule of Events for Re-entry Participants

Amendment #3 Page 12 of 42 CONFIDENTIAL

### The following revision is only applicable to U.S. sites.

### 4. SUMMARY OF STUDY DESIGN

### **Updated:**

The emerging subject safety assessments from this study will be monitored on an ongoing basis by an independent Data Safety Monitoring Board (DSMB) throughout its duration.

### 5.2 Inclusion Criteria

**Updated**: 2. Male subjects must be willing to continue use of contraception during the study. With female partners of childbearing potential, male subjects, regardless of their fertility status, must agree to either remain abstinent or use condoms in combination with one additional highly effective method of contraception (e.g., oral or implanted contraceptives, or intrauterine devices) or an effective method of contraception (e.g., diaphragms with spermicide or cervical sponges) during the study and for 14 days after study drug dosing has been completed

### 1. LIST OF ABBREVIATIONS

α7nAChR α7 nicotinic acetylcholine receptor

Aβ42 amyloid beta1-42
AD Alzheimer's disease

ADME absorption, distribution, metabolism, excretion

AE adverse event

ALP alkaline phosphatase
ALT alanine transaminase
AST aspartate transaminase
AUC area under the curve

b.i.d. twice a dayBMI Body Mass IndexBUN blood urea nitrogen

CFR Code of Federal Regulations
Cmax maximum plasma concentration

CNS central nervous system

CRO contract research organization

CSF cerebrospinal fluid CSI Cassava Sciences, Inc.

C-SSRS Columbia-Suicide Severity Rating Scale

ECG electrocardiogram

eCRF electronic case report form EDC electronic data capture

FDA Food and Drug Administration

FLNA filamin A

GCP good clinical practice

GGT gamma glutamyl transpeptidase hERG human ether-a-go-go-related gene

IB Investigator's Brochure ICF Informed consent form

ICH International Council on Harmonization of Technical Requirements

for Registration of Pharmaceuticals for Human Use

IRB Institutional Review Board LDH lactose dehydrogenase

MMSE Mini-Mental State Examination
MRI magnetic resonance imaging
NOAEL no observable adverse effect level

NOEL no observable effect level

PK pharmacokinetics

PTI-125 small molecule drug candidate to treat AD

RBC red blood cell

SAE serious adverse event

SOP standard operating procedure

ULN upper limit of normal WBC white blood cell

### 2. INTRODUCTION

### 2.1. MECHANISM OF ACTION

Cassava Sciences, Inc. (CSI) is developing simufilam, a novel drug candidate designed to treat and slow the progression of Alzheimer's disease (AD). Simufilam, through actions involving filamin A (FLNA), prevents amyloid beta1-42 (A $\beta$ 42) -induced toxic signaling cascades. A $\beta$ 42, in monomer or small oligomer form, hijacks the  $\alpha$ 7-nicotinic acetylcholine receptor ( $\alpha$ 7nAChR) and signals via this receptor to hyperphosphorylate tau. Simufilam disrupts the association between A $\beta$ 42 and the  $\alpha$ 7nAChR^1. In addition, A $\beta$ 42 persistently activates toll-like receptor 4 leading to inflammatory cytokine release and neuroinflammation. In AD mouse models, simufilam reduced cytokine release compared to control mice. We therefore expect simufilam both to improve cognition and to slow AD progression.

### 2.2. SAFETY PHARMACOLOGY AND TOXICOLOGY

A robust nonclinical ADME, safety pharmacology, and general and genetic toxicology program has been conducted with simufilam. In vitro metabolic profiling showed minimal metabolism across several species including humans. Simufilam was rapidly absorbed and eliminated in in vivo studies in rat and dog with nearly 100% oral bioavailability, a 2.67-h half-life in dog, dose-proportional PK and no accumulation. Simufilam does not inhibit or induce major CYP450 enzymes, nor is a substrate or inhibitor of major human drug transporters at clinically relevant concentrations. Safety pharmacology studies showed no adverse effects on gross behavioral and physiological parameters in the Irwin test of CNS toxicity in rats, no adverse effects on respiratory rate, tidal volume or minute volume in the rat respiratory test, and no adverse effects on arterial blood pressure, heart rate and ECG parameters in the dog cardiovascular study. The in vitro hERG test for cardiotoxicity also indicated no adverse effect. A full battery of genotoxicity studies was conducted (in vitro bacterial Ames, in vitro chromosomal aberration, and in vivo rat micronucleus test) and were all negative. An in vitro specificity screen showed no significant activation or inhibition of a panel of 68 receptors, channels, and transporters.

Simufilam was tested in single dose and repeat dose oral toxicity studies of up to 6 months in rats and 9 months in dogs. A 6-month repeat dose oral toxicity study in rats (PTI-125-NC-049) used the same doses as a 28-day study (50, 500 and 1000 mg/kg/day), which found 500 mg/kg/day to be the no-observable-adverse-effect-level (NOAEL). In the 6-month study, the toxicological response was characterized by decreased body weights and adverse structural and functional alterations in the liver of 500 and 1000 mg/kg/day animals, including increased hepatic weight, hepatocellular hypertrophy and vacuolation, single/multiple basophilic/ eosinophilic/clear cell focus, hepatocellular degeneration, pigmentation, and oval cell hyperplasia. The presence of bile pigment was consistent with

cholestasis. These findings correlated with changes to the clinical chemistry profile, including increased ALP and total/direct bilirubin. Over the 1-month recovery period, there was complete recovery of the hepatocellular degeneration and partial recovery of hepatocellular hypertrophy; other microscopic findings in the liver remained. The NOAEL in this 6-month study was 50 mg/kg/day (equivalent to 300 mg/m²), corresponding to a safety margin of 6- and 1.6-fold based on Cmax and AUC over the 100 mg b.i.d. dose in human subjects. A second 6-month repeat dose oral toxicity study in rats determined the 6-month NOAEL in the rat to be < 125 mg/kg/day, based on hepatocellular vacuolation in both sexes and hepatocellular hypertrophy in females at 125 and 250 mg/kg. We are evaluating whether these liver effects are rat specific.

In a 9-month toxicity study in dogs (PTI-125-NC-050), the no-observable-effect-level (NOEL) of simufilam was 25 mg/kg. The high dose of 200 mg/kg/day was decreased to 150 mg/kg/day after 1 month due to bodyweight loss considered unsustainable for 9 months. Clinical signs were slight hypoactivity and incidences of slight muscle fasciculations early in the study, and salivation. There were no pathology findings, but the high dose was considered adverse due to two unexplained deaths. The 75 mg/kg/day NOAEL (equivalent to 1500 mg/m²) provides 38- and 19-fold safety margins based on Cmax and AUC over the 100 mg b.i.d. dose in subjects.

Simufilam showed no mutagenic or clastogenic responses in a standard battery of genotoxicity assays.

### 2.3. CLINICAL STUDIES

A first-in-human, double-blind, single ascending dose clinical study (PTI-125-01) was conducted in healthy normal volunteers, age 18-45 with oral dosing solution. Doses were placebo, 50, 100 and 200 mg (equivalent to 31, 62, and 123 mg/m², respectively) administered to three different groups of volunteers. The study showed dose proportional PK, a half-life ranging from 4.5 to 6 h, and there were no drug-related adverse events (AEs).

In a 28-day phase 2a study (PTI-125-03), 13 subjects with mild-to-moderate AD received simufilam 100 mg b.i.d. as oral tablets. Subjects had Mini-Mental State Exam (MMSE) scores  $\geq$  16 and  $\leq$  24 and were age 50-85 with a CSF total tau/A $\beta$ 42 ratio  $\geq$  0.30. Simufilam was safe and well tolerated in all subjects.

A phase 2b randomized, placebo-controlled clinical study (PTI-125-02) of simufilam 50 or 100 mg tablets or placebo (1:1:1) enrolled 64 mild-to-moderate AD subjects with MMSE 16-26. Similar to the phase 2a study, simufilam was safe and well tolerated and no subjects discontinued due to AEs.

PTI-125-04 was a 12-month, open-label phase 2b safety study of simufilam followed by a 6-month randomized withdrawal and then an additional 6 months of open-label simufilam

administration in mild-to-moderate Alzheimer's disease subjects. Subject participation was completed in 4Q2023. Open-label adverse event data from this study is summarized in the Investigator's Brochure.

There are three ongoing Phase 3 clinical studies:

PTI-125-06 is a phase 3, randomized, double-blind, 3-arm, 76-week study investigating the safety and efficacy of 50 mg and 100 mg of simufilam, twice daily, versus placebo in slowing cognitive and functional decline in approximately 1,083 subjects with mild-to-moderate Alzheimer's disease. The assessment of neuropsychiatric symptom emergence and the impact of simufilam on CSF biomarkers represent key secondary objectives. The study is also evaluating plasma and imaging biomarkers in a series of optional sub-studies.

PTI-125-07 is a phase 3, randomized, double-blind, 2-arm, 52-week study investigating the safety and efficacy of 100 mg of simufilam, twice daily, versus placebo in slowing cognitive and functional decline in approximately 750 subjects with mild-to-moderate Alzheimer's disease. The assessment of neuropsychiatric symptom emergence is a key secondary objective. The study is also evaluating the impact of simufilam on plasma biomarkers in an optional sub-study.

PTI-125-10 is phase 3, open-label extension study evaluating the safety and long-term treatment of simufilam in mild-to-moderate Alzheimer's disease subjects. Enrollment began 4Q2022 and is only available to subjects who have completed the PTI-125-06 and PTI-125-07 protocols. The study is designed to last until the United States Food and Drug administration approves simufilam as a treatment for AD or until program termination.

### 3. STUDY OBJECTIVES

The objective of this study is to establish an open label extension following study PTI-125-04 or who already completed participation through Week 96 in PTI-125-09 to investigate the long-term safety of simufilam in subjects with mild-to-moderate AD.

### 4. SUMMARY OF STUDY DESIGN

This is an extension study of open-label simufilam 100 mg b.i.d. for subjects who completed the Phase 2 study, PTI-125-04 or who already completed participation through Week 96 in PTI-125-09. This extension study will continue through FDA approval of simufilam or program termination (Appendix A). All subjects will provide consent to enroll into this study. Simufilam will be administered as coated oral tablets.

The last study visit, Month 24, from the PTI-125-04 study will be used for the Study Day 1 visit assessments in this extension study. Clinic visits will occur every 12 weeks  $\pm 10$  days as outlined in Appendix B – Schedule of Events for Active Participants.

Subjects who already completed participation through Week 96 in PTI-125-09 will have the option to return to the study and resume participation. After the subject provides consent, the Investigator will confirm that the subject continues to satisfy both the inclusion and exclusion criteria. The study drug will be administered at the research site on Re-entry Day 1 and subsequent visits will be scheduled. The length of their participation gap will dictate which visits apply to them according to Appendix C – Schedule of Events for Reentry Participants.

For active subjects, a full physical examination (general appearance, chest/lungs, heart, abdomen, skin, musculoskeletal, Neurologic, Vascular, and Immunologic) will be performed at Study Day 1, Week 48, Week 96, and Repeat Visit B until study end. For reentry subjects, a full physical examination will occur on Re-entry Day 1 and Repeat Visit B thereafter until study ends. All subjects will return to the clinic every 12 weeks for AE monitoring, vital sign measurements, height, weight, Columbia Suicide Severity Rating Scale (C-SSRS), and drug dispensation and accountability. Some re-entry participants will require a Re-entry Week 4 visit. A brief physical exam (general appearance, cardiovascular, pulmonary, and abdominal examination, as well as an examination of any other system in response to subject-reported symptoms) will occur at all visits that do not have a full physical exam.

Blood draws for clinical laboratory testing, urine collection for urinalysis, and ECGs will be performed at Study Day 1, Weeks 24, 48, and 96, Re-entry Day 1 (if applicable), Re-Entry Week 4 (if applicable), and Repeat Visit B until study end.

Safety will be evaluated by adverse event monitoring, vital signs, clinical labs, and the C-SSRS.

The emerging subject safety assessments from this study will be monitored on an ongoing basis by an independent Data Safety Monitoring Board (DSMB) throughout its duration.

### 5. SUBJECT SELECTION

### 5.1. STUDY POPULATION

Up to 180 subjects will be enrolled in the study (male and female).

### 5.2. INCLUSION CRITERIA

All subjects must comply with the following Inclusion Criteria:

1. Must have completed the PTI-125-04 study or Week 96 in the PTI-125-09 study.

2. Male subjects must be willing to continue use of contraception during the study. With female partners of childbearing potential, male subjects, regardless of their fertility status, must agree to either remain abstinent or use condoms in combination with one additional highly effective method of contraception (e.g., oral or implanted contraceptives, or intrauterine devices) or an effective method of contraception (e.g., diaphragms with spermicide or cervical sponges) during the study and for 14 days after study drug dosing has been completed.

### 5.3. EXCLUSION CRITERIA

Subjects meeting any of the following Exclusion Criteria will be excluded from the study:

1. Anything that in the opinion of the Investigator would preclude participation in this extension study. For anyone resuming study participation, any significant medical event or hospitalization during the gap period must be discussed with the medical monitor.

### 6. STUDY DRUG

### 6.1. STUDY DRUG PHYSICAL DESCRIPTION AND PREPARATION

Investigational simufilam will be supplied by CSI as coated tablets in 188-count bottles that provide 12 weeks of b.i.d. medication. Up to 10 days of extra medication is included in each bottle.

Each used bottle of medication is to be returned to the clinic regardless of whether medication remains.

### 6.1.1. Storage

Store medication at room temperature 20°-25°C (68°-77°F), protected from moisture.

### 6.1.2. Drug Accountability

The Investigator will be responsible for monitoring the receipt, storage, dispensing and accounting of all study medications according to site SOPs. All invoices of study medication shipments must be retained in the site study file. Accurate, original site records must be maintained of drug inventory and dispensing. All records must be made available to the sponsor (or designee) and appropriate regulatory agencies upon request.

### 6.2. ADMINISTRATION AND DOSING REGIMEN

Subjects will receive 100 mg simufilam b.i.d. during the study. Simufilam tablets can be taken with or without food.

### 6.3. CONCOMITANT MEDICATIONS

Use of prescription or non-prescription medications will be recorded during the study.

### 7. STUDY PROCEDURES

Appendix B – Schedule of Events for Active Participants and Appendix C – Schedule of Events for Re-entry Participants presents the schedule of activities.

Prior to any study-related activities, the Informed Consent Form (ICF) must be signed and dated by the subject or legal authorized representative. The format and content of the ICF must be agreed upon by the Principal Investigator(s), the appropriate IRB, and the Sponsor (or designee). The signed and dated ICF must be retained by the Investigator in the subject's file.

### 7.1. STOPPING CRITERIA

Liver chemistry threshold stopping criteria have been designed to ensure subject safety and to evaluate liver event etiology during administration of study drug. Potential discontinuation of study drug for abnormal liver function tests should be considered by the Investigator in consultation with the designated medical monitor if the study subject meets one or more of the following criteria:

- ALT or AST  $\geq 4x$  ULN;
- ALT or AST  $\geq 3x$  ULN and total bilirubin  $\geq 2x$  ULN;
- ALT or AST ≥ 3x ULN if associated with the appearance or worsening of fatigue, nausea, vomiting, right upper quadrant pain or tenderness, fever, rash and/or eosinophilia; or
- ALP elevations, if deemed of liver origin and drug-related as follows:
  - o ALP > 3x ULN;
  - o ALP > 2.5x ULN and total bilirubin > 2x ULN; or
  - o ALP > 2.5x ULN if associated with the appearance or worsening of fatigue, nausea, vomiting, right upper quadrant pain or tenderness, fever, rash and/or eosinophilia.

In the event of discontinuation due to abnormal liver function tests, the subject will be appropriately investigated to determine the potential cause and referred to a physician experienced in the treatment of hepatic disorders.

Study drug should be discontinued if a subject: (1) positively affirms suicidal ideation in response to questions number 4 or 5 in the suicidal ideation section of the C-SSRS, or (2) reports any suicidal behavior or non-suicidal self-injurious behavior since their last visit in response to the C-SSRS Suicidal Behavior questions. The subject should be referred to a psychiatrist or an appropriate health care professional for further evaluation and management.

An additional stopping criterion will be bodyweight loss of  $\geq$  2 kg resulting in a BMI < 18.5.

### 7.2. EVALUATIONS BY VISIT

### 7.2.1. Study Day 1 (Dosing initiation)

Subjects who complete PTI-125-04 will be eligible to consent to this open-label extension. The Study Day 1 visit will occur in conjunction with the Month 24 visit of PTI-125-04.

Subjects will come to the clinic and, in addition to the Month 24 Visit activities for PTI-125-04, the following will be conducted:

Informed Consent

The following end of study procedures required at the Month 24 Visit for the completion of study PTI-125-04 will serve as baseline information for this open-label extension study:

- Review of concomitant medications
- Full physical examination including measurement of vital signs (blood pressure, temperature, pulse, and respiratory rate), height, weight
- C-SSRS Since Last Visit version. If the C-SSRS indicates imminent risk for suicidality, defined as the subject positively endorsing questions 4 or 5 of the suicidal ideation section or any suicidal behavior questions, discontinue study drug and refer for appropriate care.
- Blood and urine sample collection for clinical laboratory tests
- ECG
- Adverse event monitoring

Subjects will be administered one (1) tablet of study drug at the clinic. Subjects will be discharged with their supply of study drug until the next visit. They will be instructed

to take study drug twice daily, with or without food. A dose can be up to 4 hours late, but if a dose is missed, the next dose should NOT be doubled.

For all follow-up visits, subjects will be instructed to bring their study drug bottle to the clinic and a new bottle of study drug will be dispensed.

All follow-up visits can be  $\pm 10$  (ten) days for flexibility.

### 7.2.2. Follow-up Visits on Weeks 12, 36, 60, and 84

Subjects will return to clinic and the following assessments will be conducted:

- Height
- Weight
- Brief physical exam
- Measure vital signs (blood pressure, temperature, pulse, and respiratory rate)
- Adverse event monitoring
- Use of concomitant medications
- C-SSRS Since Last Visit version. If the C-SSRS indicates imminent risk for suicidality, defined as the subject positively endorsing questions 4 or 5 of the suicidal ideation section or any suicidal behavior questions, discontinue study drug and refer for appropriate care.
- Receive and count remaining tablets in each returned bottle of investigational product to assess adherence to BID dosing.

### 7.2.3. Follow-up Visits on Weeks 24 and 72

Subjects will return to clinic and the following assessments will be conducted:

- Vital signs (blood pressure, temperature, pulse, and respiratory rate)
- Height
- Weight
- Brief physical exam
- Adverse event monitoring
- Use of concomitant medications
- Clinical laboratory tests (blood and urine)
- ECG
- C-SSRS Since Last Visit version. If the C-SSRS indicates imminent risk for

suicidality, defined as the subject positively endorsing questions 4 or 5 of the suicidal ideation section or any suicidal behavior questions, discontinue study drug and refer for appropriate care.

 Receive and count remaining tablets in each returned bottle of investigational product to assess adherence to BID dosing.

### 7.2.4. Follow-up Visits on Weeks 48 and 96

Subjects will return to clinic and the following assessments will be conducted:

- Vital signs (blood pressure, temperature, pulse, and respiratory rate)
- Height
- Weight
- Full physical exam
- Adverse event monitoring
- Use of concomitant medications
- Clinical laboratory tests (blood and urine)
- ECG
- C-SSRS Since Last Visit version. If the C-SSRS indicates imminent risk for suicidality, defined as the subject positively endorsing questions 4 or 5 of the suicidal ideation section or any suicidal behavior questions, discontinue study drug and refer for appropriate care.
- Receive and count remaining tablets in each returned bottle of investigational product to assess adherence to BID dosing.

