### 9. ADVERSE EVENTS/SERIOUS ADVERSE EVENTS

### 9.1. ADVERSE EVENTS - DEFINITION

An adverse event (AE) is any undesirable event that occurs to a subject during a study, whether or not that event is considered study drug-related. Monitoring for AEs will start at dosing. Examples include:

- Any treatment-emergent signs and symptoms (events that are marked by a change from the subject's baseline/entry status [e.g., an increase in severity or frequency of pre-existing abnormality or disorder])
- All reactions from study drug, an overdose, abuse of drug, withdrawal phenomena, sensitivity, or toxicity to study drug
- Apparently unrelated illnesses
- Injury or accidents (Note: if a medical condition is known to have caused the injury or accident, the medical condition and the accident should be reported as two separate medical events [e.g., for a fall secondary to dizziness, both "dizziness" and "fall" should be recorded separately])
- Extensions or exacerbations of symptoms, subjective subject-reported events, new clinically significant abnormalities in clinical laboratory, physiological testing, or physical examination

All AEs, whether or not related to the study drug, must be fully and completely documented on the AE page of the eCRF and in the subject's clinical chart.

In the event that a subject is withdrawn from the study because of an AE, it must be recorded on the eCRF as such. The subject should be followed and treated by the Investigator until the abnormal parameter or symptom has resolved or stabilized.

The Investigator must report all directly observed AEs and all spontaneously reported AEs. The Investigator will ask the subject a non-specific question (e.g., "Have you noticed anything different since your dose of the study medication?") to assess whether any AEs have been experienced since the last assessment. AEs will be identified and documented on the eCRF in appropriate medical terminology. The severity and the relationship to the study drug will be determined and reported on the eCRF (see below).

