### 8.1. Adverse Events

The Medical Dictionary for Regulatory Activities (MedDRA) dictionary (v27.0) will be used for coding AEs on the OLE Adverse Event eCRF.

Analyses of AEs will be performed for those events that are considered treatment emergent (TEAE), where treatment emergent is defined as any AE with onset or worsening on or after the First Study Dose in the OLE study and will be summarized for overall safety population.

The following summary tables will be presented:

- Overall Summary of TEAEs
- TEAEs by system organ class (SOC) and preferred term (PT)
- TEAEs by PT
- TEAEs by SOC, PT, and Maximum Severity
- TEAEs by SOC, PT, and Relationship to Study Drug
- Treatment Emergent Serious AEs (TESAEs) by SOC and PT

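### Fully dated adverse events that began on simufilam in PTI-125-04 and continue unchanged fall in none of the AE tables or listings the SAP names, although the SAP elsewhere promises to list all eCRF data

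*Protocol*

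**What the plan says.** The only objective (Protocol 3) is "to investigate the long-term safety of simufilam in subjects with mild-to-moderate AD".

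**Baseline.** Protocol 7.2.1 states: "The Study Day 1 visit will occur in conjunction with the Month 24 visit of PTI-125-04". The procedures at that visit, including adverse event monitoring, "will serve as baseline information for this open-label extension study". Footnote b of the schedule for active participants (Protocol Appendix B; SAP Table 1) marks the Study Day 1 adverse-event cell as filled from Month 24 data.

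**Treatment before baseline.** Protocol 2.3 describes PTI-125-04 as a "12-month, open-label phase 2b safety study of simufilam followed by a 6-month randomized withdrawal and then an additional 6 months of open-label simufilam".

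**Clock.** Protocol 9.1 says: "Monitoring for AEs will start at dosing". It describes treatment-emergent signs and symptoms as "events that are marked by a change from the subject's baseline/entry status". SAP 8.1 says: "treatment emergent is defined as any AE with onset or worsening on or after the First Study Dose in the OLE study".

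**Outputs.** SAP 9 names seven AE tables (14.3.1.1 to 14.3.1.7) and four AE listings (16.2.7.1 to 16.2.7.4). Each is restricted to treatment-emergent events (TEAEs) or treatment-emergent serious events (TESAEs). SAP 7.4, 7.5 and 8.2 to 8.5 withhold listings of medical history, medications, laboratory results, vital signs, physical examination and ECG. SAP 3.1 drops the summaries of vital signs, laboratory results and ECG.

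**Text pointing the other way.** SAP 6.3.2 commits to putting everything recorded on the eCRF into the safety listings, and SAP 6.4.1 commits to listing all data by subject.

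**The concern.** A TEAE definition that starts at first dose is designed for a baseline free of study drug. Here the roll-over subjects arrive on drug. An event that simufilam may have caused in PTI-125-04, and that is still present at Month 24, becomes part of the reference status. Unless it worsens, it is not counted.

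That is a workable convention if the ongoing events are shown somewhere beside the TEAE tables. The output list in SAP 9 has no such display. Laboratory, vital-sign and ECG results are not presented either, so an abnormality present and unchanged since Month 24 has no other named safety display to appear in.

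Whether an adverse effect persists under continued treatment is part of what an extension can show. SAP 2.1 expects no full clinical study report, so these tables and listings are likely to be the main record of the study. A reader given the TEAE percentages without qualification could take them as the whole long-term profile.

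**Working it through.** The documents give no figure to reproduce on this point, and the cap of 180 subjects has no derivation. The check has three parts.

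**1. Is the baseline on-drug?** Protocol 2.3 puts six months of open-label simufilam immediately before Month 24, and Protocol 7.2.1 puts Study Day 1 at Month 24. So it is on-drug for roll-over subjects. It does not follow for Re-entry Day 1, which comes after a gap and has its own assessments and medical history (Protocol 7.2.8).

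**2. How much exposure precedes the clock?**
- PTI-125-04 has 12 months open-label, 6 months of randomized withdrawal and 6 months open-label. Assuming full adherence, no other earlier simufilam, and either no drug or continuous drug in the withdrawal period, exposure is 12 + 0 + 6 = 18 months or 12 + 6 + 6 = 24 months.
- OLE to Week 96: 96 × 7 = 672 days; 672 / 30.44 = 22.1 months.
- Share before the clock: 18 / (18 + 22.1) = 45%; 24 / (24 + 22.1) = 52%.

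**3. Where does an unchanged parent-study event land?** The start-date rules of SAP 6.3.2 were applied to an event that began in PTI-125-04 and continues at the same severity. The first OLE dose is assumed to be 15 September 2022, for illustration only.

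| Start date recorded | Date used under SAP 6.3.2 | Result |
|---|---|---|
| 10 May 2022 (complete) | 10 May 2022 | not a TEAE |
| 10 May 2021 (complete) | 10 May 2021 | not a TEAE |
| 2022 only | 15 Sep 2022 | TEAE |
| 2021 only | 1 Jan 2021 | not a TEAE |
| day 20, 2022, month missing | 20 Sep 2022 | TEAE |
| day 5, 2022, month missing | 5 Jan 2022 | not a TEAE |
| Sep 2022, day missing | 15 Sep 2022 | TEAE |
| May 2022, day missing | 1 May 2022 | not a TEAE |
| wholly missing | none | TEAE if the end date is on or after first dose |

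The last rule needs an end date, so it does not settle the case of an event still ongoing with no end date.

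Setting these results against SAP 9, a fully dated event enters none of Tables 14.3.1.1 to 14.3.1.7 and none of Listings 16.2.7.1 to 16.2.7.4. The same event with certain incomplete dates enters the TEAE tables. Whether it is reported thus depends on how completely the date was recorded.

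**The case against.** Several points on the other side are sound.

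- **The SAP promises to list everything.** Where it withholds a type of data it usually says so, and it never says that AEs which are not TEAEs will be left out. This stands to the extent that a reader cannot infer that such events appear in no output at all. But the general sentences sit beside explicit exclusions of medications, laboratory results and other data, so they cannot be relied on to override the specific list in SAP 9. The SAP conflicts with itself.
- **Some of these events would still surface.** Certain incomplete dates make them TEAEs, and one that ended treatment could appear as a discontinuation reason under SAP 7.1, which has no TEAE restriction. This is correct, but neither route is systematic.
- **Entry limited to completers is inherent in an extension.** SAP 7.1 sets the number dosed in PTI-125-04 beside the number enrolled here, so attrition is visible. Selection is therefore something to state in a footnote, not a fault of the analysis.
- **The occurrence of these events is not lost to the programme.** Protocol 2.3 says open-label PTI-125-04 adverse events are summarized in the Investigator's Brochure. What the SAP's named outputs lack is their presence at entry and their course during the extension.
- **Onset or worsening from first OLE dose is a coherent, stated rule.** It is, and it need not change. It needs a companion display.

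A reader might also infer that the percentages will look better than those of the parent study, or will mislead the DSUR. The documents do not support that. No comparison with PTI-125-04 is planned, SAP 2.2 says only that results may be used in the DSUR, and neither the DSUR nor the parent protocol is available.

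**Conclusion.** The point holds for subjects rolling over from PTI-125-04. Their baseline is on-drug, the clock restarts at the first OLE dose, and a fully dated, unchanged parent-study event is in no AE table or listing named in SAP 8.1 and 9. SAP 6.3.2 and 6.4.1 contradict that list, and the date rules treat identical events differently.

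The 45% to 52% shows how much exposure to Week 96 lies before the clock, on the assumptions stated with the calculation. It should not be read as a share of events missed or as a measure of bias. The documents give no count of subjects with an AE ongoing at Study Day 1, so the number affected is unknown.

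The on-drug statement should not be extended to Re-entry Day 1. The change is worth making because safety is the only objective and the remedy is small.

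**What to change.** 1. Change Listing 16.2.7.1 from TEAEs to all AEs in the OLE database, with a TEAE flag that also shows when the status rests on an imputed start date. Include AEs ongoing at Study Day 1 from the Month 24 data that footnote b already brings in, with last recorded status where captured.
2. Add a simple count, by SOC and PT, of subjects with an AE ongoing at first OLE dose.
3. Reconcile SAP 6.3.2 and 6.4.1 with SAP 8.1 and 9, so that the promise to list data matches the listings named.
4. Footnote the TEAE tables: percentages are events new or worsened since the first OLE dose in subjects who completed PTI-125-04, and exclude AEs ongoing at entry.

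The cost is SAP wording, a little programming, and MedDRA coding of the Month 24 events where needed. The display becomes slightly less favourable. No new data collection is required. A full reconstruction of PTI-125-04 AE history with outcome at last OLE contact is not proposed: SAP 8.1 covers the OLE adverse event eCRF, and nothing in the documents shows that every ongoing parent-study event was carried onto it and followed.
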